**ORAL RPV**

For safety and risk mitigation for oral RPV refer to the RPV local prescribing information .

**RPV LA**

Information about the clinical experience to date and possible risks associated with treatment using RPV LA can be found in the Summary of Data and Guidance for the Investigator section of the IB. Systemic reactions following RPV LA injections have been observed in clinical trials. These occur infrequently (in less than 0.5% of participants) and typically begin to resolve within minutes of the injection however, some participants required supportive care. Where timely PK data was available, high RPV PK plasma concentrations have been observed which may have resulted from an accidental partial IV injection of RPV. The following risks are considered to be of specific clinical relevance in the context of IM use.

Potential Risk of Clinical Significance	Summary of Data/Rationale for Risk	Mitigation Strategy
Injection Site Reactions	Clinical, experience to date has demonstrated ISRs occur in the majority of exposed participants treated with RPV LA but are generally mild (Grade 1) or moderate (Grade 2) and include events of pain, tenderness, erythema, or nodule formation of several days duration (median duration for individual events <1 week). ISRs may occur more than once in an individual participant receiving multiple injections. Although some Grade 3 ISRs were reported, overall ISRs have been well tolerated and have not to date been associated with an excess of participants' withdrawal due to ISRs.	
 
• Administration advice to minimize risk of poor administration technique giving rise to injection site reactions. Advice on care, monitoring, natural course, and treatment of ISRs given in study documentation.
 
• Advice to participants on care of injection site on day/days immediately post administration, use of analgesia, compresses where appropriate.
 
• Participants will be closely monitored for ISRs particularly for signs of pain, tenderness, infections, erythema, swelling, induration, or nodules (granulomas or cysts) throughout the
 

Potential Risk of Clinical Significance	Summary of Data/Rationale for Risk	Mitigation Strategy
	
None of the ISRs was serious and no clinical significant complications were reported
	
study.
 
 
• Complications of ISRs such as infections (abscess, cellulitis) and collections of fluid requiring drainage will be monitored
 
• Significant ISRs may be photographed and referred to a dermatologist for specialist advice.
 

Rash
	
Some observations of rash with oral RPV have been reported in clinical studies executed to date (the majority are Grade 1 or 2).
 
Severe skin and hypersensitivity reactions have been reported during the postmarketing experience, including cases of Drug Reaction with Eosinophilia and Systemic Symptoms (DRESS), with oral RPV containing regimens. While some skin reactions were accompanied by constitutional symptoms such as fever, other skin reactions were associated with organ dysfunctions, including elevations in hepatic serum biochemistries.
	
 
• In this study, RPV LA administration will be preceded by an oral RPV lead in to evaluate safety and tolerability in individual participants.
 
• Participants with a Grade 1 or 2 rash will be allowed to continue treatment , depending on the clinical judgment of the investigator.
 
• All participants experiencing a Grade 3 or 4 rash should discontinue their ARV medication (study medication and background regimen) and be withdrawn from the study.
 
• All rash events should be assessed with special attention to systemic symptoms, laboratory abnormalities, or mucosal involvement. Close clinical follow-up, including follow-up of laboratory abnormalities, and appropriate medical intervention, including referral to
 

Potential Risk of Clinical Significance	Summary of Data/Rationale for Risk	Mitigation Strategy
		
dermatologist as appropriate, should be instituted for these events; daily follow-up is recommended for 5 days from the onset of the event to monitor for progression of the event. See Section 7.4.5.13 for additional guidance on management of rash events.

Development of Resistance	
Residual concentrations of RPV LA can remain in the systemic circulation of participants who stopped treatment (e.g., for tolerability issues or treatment failure) for prolonged periods (months to more than a year, in some subjects, McGowan, 2016).
 
Participants discontinuing a LA regimen may be at risk for developing resistance to RPV many weeks after discontinuing injectable therapy.
	
 
• After participants stop RPV LA, Oral HAART regimens will be prescribed within 4 weeks after the last Q4W dose or within 8 weeks after the last Q8W dose, and following consultation with the medical monitor. This would be anticipated to result in rapid resuppression of HIV-1 RNA thus minimizing the risk of emergent resistance
 
• The Sponsor will continue to monitor participants in this study who discontinue a LA regimen for a minimum of 52 weeks from the time of the last LA administration.
 

Drug-Drug Interactions (DDIs)	
For a complete listing of permitted and prohibited concurrent medications for RPV and RPV LA, refer to Section 6.13
 
RPV LA should not be co-administered with the following medicinal products, as significant decreases in RPV plasma concentrations may occur (due to CYP3A enzyme induction), which
	
 
• All participants will be informed of prohibited medications throughout the study and updates provided as needed via informed consent.
 

Potential Risk of Clinical Significance	Summary of Data/Rationale for Risk	Mitigation Strategy
	
may result in loss of therapeutic effect of RPV LA.
 
 
- the anticonvulsants carbamazepine, oxcarbazepine, phenobarbital, phenytoin
 
- the antimycobacterials rifampicin, rifapentine, rifabutin
 
- the glucocorticoid systemic dexamethasone, except as a single dose treatment
 
- St John’s wort (Hypericum perforatum).
 
 
Of note, evidence to date indicates that clinically relevant DDIs with RPV LA and other antiretrovirals are unlikely to occur.
 
Oral RPV administration only:
 
 
- Antacid products containing divalent cations (e.g., aluminum, calcium, and magnesium) must be taken at least 2 hours before or at least 4 hours after RPV.
 
- H2-antagonists must be taken at least 12 hours before or at least 4 hours after taking RPV.
 
- RPV should not be co-administered with proton pump inhibitors, such as esomeprazole,
 
	

Potential Risk of Clinical Significance	Summary of Data/Rationale for Risk	Mitigation Strategy
	
lansoprazole, omeprazole, pantoprazole, rabeprazole;
 
Participants discontinuing a LA regimen may be at risk for developing DDIs many weeks after discontinuing injectable therapy.
	

Potential Risk of Clinical Significance	Summary of Data/Rationale for Risk	Mitigation Strategy

Inadvertent Intravenous Injection (Accidental Maladministration)
	
As with any intramuscular injection, it is possible that RPV LA can be inadvertently administered intravenously instead of intramuscularly possibly resulting in higher than expected concentrations of RPV shortly after injection and lower concentrations thereafter. This could be due to administrator error, improper injection technique and / or improper needle length used based on body type.
 
In addition, HIV-1 viral suppression may not be effective following accidental intravenous maladministration.
 
Systemic reactions following RPV LA injections have been observed in clinical trials. These occur infrequently (in less than 0.5% of participants) and typically begin to resolve within minutes of the injection, however some participants required supportive care. Where timely PK data was available, high RPV PK plasma concentrations have been observed which may have resulted from an accidental partial IV injection of RPV
	
 
• Training will be provided to all sites on proper injection technique.
 
• Should IM maladministration be suspected at any time (e.g., suspected under or overdose or inadvertent IV dosing), post dose ECG monitoring and vital signs or any other supportive testing may be obtained at the discretion of the investigator, and the medical monitor notified
 
• Laboratory samples for safety parameters and HIV-1 RNA will be closely monitored in all participants. Additionally, 2-hour post dose PK samples will be obtained at a few early timepoints for determination of RPV concentration and possible pharmacokinetic correlation with safety parameters such as ECG changes and virologic response. Additionally, an unscheduled PK sample may be drawn approximately 2 hours post dosing for future evaluation of RPV concentrations.
 

Potential Risk of Clinical Significance	Summary of Data/Rationale for Risk	Mitigation Strategy
Other Study Related Risks		
Venipuncture	Participants will be required to have blood samples taken. Risk of bruising, and rarely, infection	
 
• Trained personnel will perform venipuncture
 

Risks of ECG pad removal	
Participants will be required to have ECG tracings recorded periodically throughout the study
 
Some discomfort and rash may occur where the ECG pads are removed.
	
 
• ECGs will be conducted by appropriately trained personnel and effort made to minimize contact time for application of the pads.
 

Risk of Treatment Failure	
This study employs a novel 2 drug LA ART maintenance regimen for the treatment of HIV-1 infection that remains experimental. Both IM CAB and RPV have demonstrated antiviral activity in large clinical studies and the two drug combination dosed Q4W has demonstrated sustained antiviral activity in studies 200056, 201584 and 201585 however the efficacy of Q8W dosing remains under evaluation.
 
Doses of the CAB LA and RPV LA have been selected to achieve exposures that are expected to maintain virologic efficacy on the basis of available data with the oral and LA formulations.
	
 
• Viral loads and CD4+ cell counts will be closely monitored throughout the study (maintenance and extension phases), allowing for early detection of failing treatment. Where confirmed virological failure occurs, participants would be discontinued from study drugs and transferred to an oral HAART regimen.
 
• Plasma samples will be collected throughout the Maintenance Phase for determination of CAB and RPV concentration and possible pharmacokinetic correlation with virologic response.
 

Potential Risk of Clinical Significance	Summary of Data/Rationale for Risk	Mitigation Strategy
	
Due to administration error, it is possible that a participant could receive an inadequate dose of CAB LA or RPV LA. Sub-therapeutic concentrations of either CAB LA or RPV LA could lead to virologic failure and possibly the development of viral resistance.
	

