**Participants must be discontinued from study treatment for any of the following reasons:**

- Participants who are not eligible to continue into the Maintenance Phase.
- Participants who are not eligible, or do not wish to continue on to the Extension Phase.
- Virologic withdrawal criteria as specified in Section 5.5.4 are met;
- Participant requires substitution of ART;
- Participant requires substitution or dose reduction of CAB LA or RPV LA (oral bridging supply and potential for a second loading dose may be permissible following discussion with the Medical Monitor).
- Liver toxicity where stopping criteria are met and no compelling alternate cause is identified (see Section 5.5.1);
- Renal toxicity are met and no compelling alternate cause is identified;
- QT interval (QTc) interval >550 msec from three or more tracings separated by at least 5 minutes and considered causally related to IP.
- Grade 4 clinical AE considered causally related to study drug;
- Participant has a Grade 3 or higher rash or Grade 2 rash with evidence of systemic involvement and no compelling alternative cause is identified
- Participant withdrew consent

Efficacy data for participants withdrawing from the study will be considered evaluable up to the point at which they are withdrawn using the same criteria for evaluability as for participants who complete the study.

Safety data for all participants who receive any amount of study drug, including participants who withdraw from the study, will be included in evaluations of safety.

All data from the Withdrawal visit will be recorded, as they comprise an essential evaluation that should be done prior to discharging any participant from the study.

The following actions must be taken in relation to a participant who fails to attend the clinic for a required study visit:

- a. The site must attempt to contact the participant and re-schedule the missed visit as soon as possible.
- b. The site must counsel the participant on the importance of maintaining the assigned visit schedule and ascertain whether or not the participant wishes to and/or should continue in the study.

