#### **7.4.4.2. Grade 1 or Grade 2 Toxicity/Adverse Event**

Participants who develop a Grade 1 or Grade 2 AE or toxicity may continue study drug at the discretion of the investigator. Participants who choose to withdraw from the study due to a Grade 1 or 2 AE should have study withdrawal and follow-up evaluations completed.

**Participants who develop ALT  $\geq$ 3 times ULN while on study must consult with Medical Monitor prior to initiation or continuation of CAB LA + RPV LA**

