#### **7.4.4.3. Grade 3 Toxicity/Adverse Event**

Participants who develop a Grade 3 AE or toxicity should be managed as follows:

- If the Investigator has compelling evidence that the Grade 3 AE or toxicity has not been caused by IP, dosing may continue after discussion with the Medical Monitor.
- Participants who develop a Grade 3 AE or toxicity, which the Investigator considers related or possibly related to the IP, should have the IP withheld and be rechecked each week until the AE returns to Grade 2. Once the AE is Grade  $\leq$ 2, IP may be re-started.
- Should the same Grade 3 AE recur within 28 days in the same participant, the IP should be permanently discontinued and the participant withdrawn from study.
- Participants experiencing Grade 3 AEs requiring permanent discontinuation of IP should be followed weekly until resolution of the AE and to have withdrawal study evaluations completed. A follow-up visit should be performed 2-4 weeks after the last dose of IP. Any participant receiving at least one dose of CAB LA and /or RPV LA who discontinue IP / Withdraw will initiate treatment with HAART and enter the LTFU Phase for 52 weeks of follow up.
- Participants with Grade 3 asymptomatic laboratory abnormalities should be investigated for all potential non-drug related causes, and, following discussion with the Medical Monitor, may continue IP if the Investigator has compelling evidence that the toxicity is not related to IP, with the exception of liver chemistry stopping criteria (See Section 7.4.5.1). Isolated Grade 3 lipid abnormalities do not require withdrawal of IP.

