#### 7.4.4.4. Grade 4 Toxicity/Adverse Event

- Participants who develop a Grade 4 AE or toxicity must have IP permanently discontinued. However, if the Investigator has compelling evidence that the AE is not causally related to the IP, dosing may continue after discussion with, and assent from, the Medical Monitor. Participants should be rechecked each week until the AE returns to Grade 2.
- Participants experiencing Grade 4 AEs requiring permanent discontinuation of IP should be followed weekly until resolution of the AE and encouraged to complete the withdrawal and follow-up study evaluations as noted above. Any participant receiving at least one dose of CAB LA and /or RPV LA who discontinue IP / Withdraw will initiate treatment with HAART and enter the LTFU Phase for 52 weeks of follow up.
- Participants with Grade 4 asymptomatic laboratory abnormalities should be investigated for all potential non-drug related causes, and, following discussion with the Medical Monitor, may continue therapy if the Investigator has compelling evidence that the toxicity is not related to IP, with the exception of liver chemistry stopping criteria (See Section 7.4.5.1). An in-clinic follow-up visit will be performed approximately 2-4 weeks after the last dose of study medication if AEs, SAEs, or laboratory abnormalities considered potentially harmful to the participant are ongoing at the last on-study visit. Isolated Grade 4 lipid abnormalities do not require withdrawal of IP.

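### The rash rules do not agree on Grade 2 rash with systemic involvement, or on Grade 3-4 rash with another cause

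*Protocol*

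**What the plan says.** Three parts of the protocol bear on what happens to study treatment when a participant develops a rash.

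- **Section 2.3.1 (risk table, RPV LA, Rash).** For the lower grades: "Participants with a Grade 1 or 2 rash will be allowed to continue treatment"; the sentence goes on to make this a matter for the investigator's clinical judgement. For the higher grades: "All participants experiencing a Grade 3 or 4 rash should discontinue their ARV medication (study medication and background regimen) and be withdrawn from the study". The higher-grade sentence has no exception for cause. The entry then refers to Section 7.4.5.13 for further guidance.
- **Section 5.5 (Withdrawal/Stopping Criteria).** Under the lead-in "Participants must be discontinued from study treatment for any of the following reasons", one item reads: "Participant has a Grade 3 or higher rash or Grade 2 rash with evidence of systemic involvement and no compelling alternative cause is identified".
- **Section 7.4.4 (Toxicity Management), by grade.** Section 7.4.4.2: "Participants who develop a Grade 1 or Grade 2 AE or toxicity may continue study drug at the discretion of the investigator". Section 7.4.4.3: "If the Investigator has compelling evidence that the Grade 3 AE or toxicity has not been caused by IP, dosing may continue", once the Medical Monitor has been consulted. Section 7.4.4.4: "if the Investigator has compelling evidence that the AE is not causally related to the IP, dosing may continue", once the Medical Monitor has been consulted and has agreed.

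Section 7.4.5.13, the dedicated rash section, lies in the part of the protocol that was not supplied for this review.

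**The concern.** A stopping rule should give one answer for a given participant. Here the answer can depend on which section a site opens. The risk table itself notes post-marketing reports of severe skin and hypersensitivity reactions with oral RPV regimens, some with fever and some with organ dysfunction. Elsewhere in Section 2.3.1 the protocol says that both drugs can stay in the circulation for more than a year in some participants after the last injection. Whether a further injection may be given is therefore a decision that cannot quickly be undone.

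The main stakes are participant safety and uniform conduct across sites. A lesser one is measurement: the proportion of participants who discontinue because of adverse events is a secondary endpoint in Section 3, and sites that apply different rules to the same rash would contribute to it differently.

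**Working it through.** No stated figure is involved, so there is nothing to recompute. The check is to take each combination of grade, systemic involvement and cause, and read off what each section requires.

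1. **Grade 2, systemic involvement, no compelling alternative cause.** Sections 2.3.1 and 7.4.4.2 leave continuation to the investigator. Section 5.5 requires discontinuation. However the last clause of the Section 5.5 item is parsed, it covers this participant, so no reading avoids the conflict. A site that stops treatment satisfies all three sections. A site that relies on Section 2.3.1 or 7.4.4.2 alone is not told that stopping is mandatory.

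2. **Grade 2, no systemic involvement.** Sections 2.3.1 and 7.4.4.2 give discretion, and the Section 5.5 rash item is not triggered. No conflict.

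3. **Grade 3-4, no compelling alternative cause.** Sections 2.3.1 and 5.5 both stop study treatment. They differ on status: Section 2.3.1 withdraws the participant from the study, whereas Section 5.5 speaks only of study treatment. Section 4.2.4 places participants who stop for safety reasons after an injection in a 52-week follow-up phase that it counts as study participation. Section 7.4.4.3 also has a general route to withhold and later restart after a possibly related Grade 3 event. Its relation to the rash rules should be stated in the same edit.

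4. **Grade 3-4, compelling alternative cause.**
   - Section 2.3.1 stops and withdraws all participants.
   - Sections 7.4.4.3 and 7.4.4.4 allow dosing to continue after Medical Monitor discussion (Grade 3) or discussion and assent (Grade 4).
   - Section 5.5 can be parsed in two ways. If the alternative-cause clause applies only to Grade 2 with systemic involvement, Section 5.5 agrees with Section 2.3.1 that treatment stops, and both differ from Section 7.4.4. If the clause applies to Grade 3 and above as well, Section 5.5 does not mandate stopping, but it does not say that treatment continues either.
   - On either parsing, Section 2.3.1 and Sections 7.4.4.3-7.4.4.4 differ.

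Two combinations, 1 and 4, therefore lack a single instruction on study treatment for the reasons raised here. In combination 4 the mandatory criterion is itself ambiguous.

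**The case against.** The case on the other side has four parts.

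- **The risk table is conditional.** A reader might infer that it lets all Grade 2 rash continue. It does not: permission depends on the investigator's judgement, and the same entry asks for special attention to systemic symptoms, laboratory abnormalities and mucosal involvement. The CAB hypersensitivity row in Section 2.3.1 also bars further injections when hypersensitivity is suspected, which would catch some Grade 2 rashes with systemic features. This stands, and it narrows combination 1 to discretion against a mandate. It does not close the gap, because the hypersensitivity row turns on suspicion of that diagnosis and Section 5.5 does not.
- **Sections 2.3.1 and 5.5 need not clash at Grade 3-4.** A reader might infer that they give opposite instructions when there is another cause. The documents do not support that as a definite statement. It depends on how far the last clause of the Section 5.5 item reaches, and even the wider reading only leaves stopping unmandated. The firmer conflict is with Sections 7.4.4.3 and 7.4.4.4. Those are general rules, and specific toxicities are handled in Section 7.4.5, but none of the sections compared here says which prevails for rash.
- **Section 7.4.5.13 may settle precedence.** This is fair. A detailed rash section could state the full rule, so it would be wrong to say that no further section could help. The risk table cites it only as additional guidance, however, and the sentences above would still differ from one another.
- **The Medical Monitor limits divergence.** Section 6.9 requires decisions on interrupting or resuming dosing to be discussed with the Medical Monitor in advance. This reduces inconsistency between sites. It does not tell the Medical Monitor which section to apply.

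**Conclusion.** The point holds as an inconsistency in the rash rules, limited to two situations. For Grade 2 rash with systemic involvement and no compelling alternative cause, investigator discretion (Sections 2.3.1 and 7.4.4.2) stands against mandatory discontinuation (Section 5.5). For Grade 3-4 rash with a compelling alternative cause, universal stopping and withdrawal (Section 2.3.1) stands against permitted continuation (Sections 7.4.4.3 and 7.4.4.4), while the reach of the Section 5.5 clause is unclear.

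The size cannot be given in numbers. The material reviewed states no rash rate, so the number of participants affected and any effect on discontinuations due to adverse events cannot be estimated and may be small. Sample size, power and alpha are not affected. The conclusion rests on the sections available. If Section 7.4.5.13 sets out a full rule and its precedence, the practical risk is smaller, but the conflicting sentences would still need aligning. No view is taken on which clinical rule is right.

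**What to change.** Reconcile Sections 2.3.1, 5.5, 7.4.4.2-7.4.4.4 and 7.4.5.13 so that each combination of grade, systemic involvement and alternative cause carries one instruction. In doing so:

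- split the Section 5.5 item so that it is explicit whether the alternative-cause condition applies to Grade 3 and above, to Grade 2 with systemic involvement, or to both;
- name the section that governs rash and have the others cross-refer to it instead of restating the rule;
- use the same terms throughout for stopping study treatment and for leaving the study.

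The choice of rule belongs to the sponsor's clinical team. The cost is amendment wording and a clarification letter to sites. The design and the planned analyses do not change.
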